Consent will be obtained at time of admission to Labor & Delivery. Randomization to either the oxygen group or room air group will be performed when the patient is in active labor (defined as regular contractions and  $\geq 6$  cm cervical dilation) and develops Category II FHT necessitating intrauterine resuscitation as determined by the care provider team (Figure 3). This will be performed via a computer-generated randomization sequence in a 1:1 ratio. Patients randomized to the oxygen group will receive the above stated current management of oxygen via nonrebreather face mask at 10L/min and “per-protocol” defined as receiving the mask for at least 90% of the remaining duration of labor including during cesarean delivery. Patients randomized to the room air group will not receive oxygen for Category II FHT unless otherwise required for maternal indications. Alternative and/or additional intrauterine resuscitation techniques for both groups (i.e. fluid bolus, maternal repositioning, and discontinuation of oxytocin) will be left to

the discretion of the medical team. The initial 6 patients consented and randomized will be part of a compliance run-in with the same protocol as above.

[figure not shown]

Figure 3: Flow diagram for randomization and treatment groups  
 L&D: Labor and Delivery FHT: fetal heart tracing

Specific Aim 1: Determine the effect of maternal oxygen administration for Category II FHT on neonatal cord gas parameters

After delivery of the infant, a segment of the umbilical cord will be removed with immediate collection of umbilical artery and vein samples by trained providers. These samples will be sent to the hospital laboratory for routine cord gas measurements as is universally practiced on our Labor and Delivery unit.

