## **Statistical Analysis**

Intention-to-treat (primary analysis) and per protocol analyses will be performed. Chi-squared and Fisher's exact tests will be used to compare categorical variables as appropriate. Continuous variables will initially be assessed for distribution pattern via the Kolmogorov-Smirnov test. Normally distributed variables will be compared using Student's t-tests and non-normally distributed variables will be analyzed with the Mann-Whitney U test. These analyses will be supplemented by multivariable logistic regressions to adjust for confounders.

Tests with  $p < 0.05$  will be considered statistically significant. Analyses will be performed using Stata (Stata Corp., College Station, TX).

For the primary outcome of lactate, 95% confidence intervals (CI) will be calculated for the mean cord lactate levels in each group. Comparison of the 95% CI in each group will then determine non-inferiority or inferiority.

Additional interaction analyses for the primary outcome will be performed for the following subgroups:

- 1) Presence of chronic medical conditions (hypertensive disorder, diabetes)

- a. Patients with hypertensive disorders (chronic hypertension, gestational hypertension, preeclampsia)
- b. Patients with diabetes mellitus (gestational diabetes, T1DM, T2DM)
- 2) Recurrent late decelerations pre intervention
- 3) Recurrent variable decelerations pre intervention
- 4) Prolonged deceleration pre intervention
- 5) Fetal tachycardia pre intervention
- 6) Fetuses with intrauterine growth restriction
- 7) Chorioamnionitis
- 8) Within oxygen group: Duration of oxygen exposure
  - a. <50% of total duration of active labor (onset of active labor to delivery)
  - b. >50% of total duration of active labor (onset of active labor to delivery)

Odds ratios and 95% CI will be calculated for the secondary outcome of persistent Category II FHT. Kaplan-Meir analyses will be performed for fetal monitoring analyses.

For the outcome of maternal and cord blood MDA, a fetal MDA will be calculated by subtracting umbilical artery MDA from maternal MDA for each sample. The calculated mean fetal MDA and maternal MDA values will then be compared between groups using either Student t test or Mann Whitney U test.

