### **Sample size analysis**

A review of previously collected data from our institution of 5182 term singleton pregnancies revealed a mean cord lactate of  $3.5 \pm 1.6$  mmol/L in women with Category II FHT within 30 minutes of delivery. All of these deliveries were managed using our current protocol of routine oxygen administration for Category II FHT. Given the normal mean lactate seen in our population of patients with Category II FHT, a noninferiority approach was selected to test our hypothesis that room air is not inferior to oxygen administration in treating Category II FHT. A total sample size of 98 patients will be needed to detect a non-inferiority margin of 30% with 90% power, using a one-sided two-sample t-test (alpha 0.025). To accommodate a 15% drop out/cross over rate, a total of 114 patients will be needed. We plan on performing an initial compliance run-in of 6 patients making the total enrollment 120 patients. Data analysis will only be performed on the 114 patients enrolled after the initial 6 patients enrolled/randomized in the compliance run-in/pilot. Previous studies have shown an increased risk for neonatal morbidity with cord lactate cut-offs ranging from 3.2-6.0. The margin of noninferiority was

therefore set at a lactate cut-off of 4.5, above which there is a clear association with neonatal morbidity.

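### The primary non-inferiority rule compares separate per-arm 95% CIs, with no success criterion, no between-arm difference and no margin, so the planned 2.5% error and 90% power do not carry over to it.

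*Combined protocol and SAP*

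**What the plan says.** The Statistical Analysis section has two sentences on how the primary outcome is decided. First, "95% confidence intervals (CI) will be calculated for the mean cord lactate levels in each group". Then, "Comparison of the 95% CI in each group will then determine non-inferiority or inferiority". The rest of that section gives general rules for all variables. Normally distributed continuous variables get a t-test, while "non-normally distributed variables will be analyzed with the Mann-Whitney U test". The only adjusted analysis named is in the sentence "These analyses will be supplemented by multivariable logistic regressions to adjust for confounders".

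The Sample size analysis section describes a different procedure: "A total sample size of 98 patients will be needed to detect a non-inferiority margin of 30% with 90% power", with the method given as "using a one-sided two-sample t-test (alpha 0.025". It ends by saying that the margin was "therefore set at a lactate cut-off of 4.5, above which there is a clear association with neonatal morbidity". No section connects this test or this margin to the comparison of per-arm CIs.

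**The concern.** A non-inferiority claim concerns the difference between arms relative to a margin. Two separate CIs do not give the interval for that difference, and the text does not say what pattern in them means success. At least four readings are open, where success means:

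- (a) the two CIs overlap;
- (b) the room-air upper limit is below 4.5;
- (c) the room-air upper limit is below the oxygen lower limit plus the margin;
- (d) the room-air upper limit is below 1.3 times the observed oxygen mean.

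None of these is the test on which the trial was sized. The margin is also not a single number: 30% of 3.5 is 1.05 mmol/L, while 4.5 − 3.5 is 1.0 mmol/L. This rule produces the trial's main conclusion, so the same data could support opposite verdicts depending on a reading chosen afterwards. A false claim of non-inferiority would support withholding what the protocol describes as current practice.

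**Working it through.** **Inputs.** From Sample size analysis: oxygen-arm mean 3.5, SD 1.6, one-sided alpha 0.025, power 90%, margin 30%, cut-off 4.5, 98 evaluable patients, 114 after the allowance for drop-out and cross-over. From Strategy: "computer-generated randomization sequence in a 1:1 ratio", so 49 per arm evaluable, or 57 per arm if none of the 114 is lost. Assumption: the true difference is zero in the power calculation. The plan does not state this, but it returns the plan's N.

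**Reproducing the plan's figure.** n per arm = 2(z₀.₉₇₅ + z₀.₉₀)² SD² / margin².

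- Margin 1.05: 2 × (1.960 + 1.282)² × 1.6² / 1.05² = 48.8, so 49 per arm and 98 in total. This matches. Noncentral-t power is 89.5% at 49 per arm and 93.5% at 57.
- Margin 1.0: 53.8, so 54 per arm and 108 in total. This does not match. Noncentral-t power is 86.5% at 49 per arm and 91.1% at 57, and 90% is reached at 55 per arm (110).

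The sized test is therefore the difference in means against 1.05.

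**Precision.** Per-arm CI half-width = t × 1.6/√n = 0.460 at n = 49 and 0.425 at n = 57. SE of the difference = 1.6 × √(2/n) = 0.323 and 0.300.

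**Operating characteristics.** Simulation of means and SDs, 1,000,000 trials per scenario, normal data, SD 1.6, oxygen mean 3.5. Error is the chance of declaring non-inferiority at a true deficit of 1.05. Power is that chance at no difference. Results are for 49 (57) per arm.

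| Reading | Error | Power |
|---|---|---|
| (a) CIs overlap | 34% (25%) | 99.7% (99.7%) |
| (b) Room-air upper limit < 4.5 | 1.5% (1.4%) | 99% (99.6%) |
| (c) Room-air upper limit < oxygen lower limit + 1.05 | 0.3% (0.3%) | 66% (75%) |
| (d) Room-air upper limit < 1.3 × observed oxygen mean | 11% (11%) | 94% (96%) |
| CI of the difference, upper limit < 1.05 | 2.5% (2.5%) | 89.5% (93.5%) |

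At a true deficit of 1.0, reading (a) passes 40% (31%) of the time and reading (b) 2.5% (2.5%).

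Reading (b) behaves well at the planning values but depends on the oxygen mean being 3.5. With assumed oxygen means of 3.25 and 3.0, and room air still 1.05 worse, it passes 14% (15%) and 49% (55%) of the time. With an assumed mean of 4.0 in both arms, its power is 57% (64%). The CI of the difference against a fixed 1.05 is unaffected by the oxygen mean.

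**One data set, two verdicts.** Take 57 per arm, SD 1.6 and observed means of 3.4 (oxygen) and 4.0 (room air).

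- Per-arm CIs: 3.4 ± 0.425 = 2.98 to 3.82, and 4.0 ± 0.425 = 3.58 to 4.42. They overlap and 4.42 < 4.5, so (a) and (b) both declare non-inferiority.
- Difference: 0.6 ± 1.981 × 0.2997 = 0.006 to 1.194. The upper limit exceeds both 1.0 and 1.05, so non-inferiority fails. The lower limit is above zero, so room air is significantly worse.

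**Normality branch.** If lactate were gamma or lognormal with mean 3.5 and SD 1.6 (assumed), the Kolmogorov-Smirnov test at N = 98 would reject normality in 5–26% of trials with the standard table, or 58–87% with the Lilliefors correction. The plan's alternative, Mann-Whitney, carries no margin. In the gamma case the CI of the difference still has 2.5% error and 89.4% (93.3%) power.

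**The case against.** The strongest reply is that the intended analysis can be inferred. A one-sided 0.025 test corresponds to a two-sided 95% CI of the difference, and the margin is in the plan, so a careful statistician would run the right test. That makes the repair easy, but nothing in the plan requires that test, and the sentence that decides the outcome names another procedure.

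Second, the largest error belongs to the overlap reading, which the plan never mentions, and the 4.5 reading is closer to its wording. This is fair. Reading (b) does well at an oxygen mean of 3.5, and (c) is conservative on error and costs only power. An undefined rule also has no single error rate.

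Third, reading (b) tests whether the room-air mean is below 4.5. With oxygen at 3.0 and room air at 4.05, passing is correct for that hypothesis; with room air truly at 4.5, its error is 2.5%. This also stands. The 14% and 49% are errors only against a fixed deficit of 1.05, and the oxygen means behind them are assumed. What remains is that (b) ignores the concurrent control arm.

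Fourth, if 30% is meant as a relative margin, an oxygen mean of 3.0 makes it 0.9, and a test against 1.05 then has about 6.7% error at 49 per arm (7.1% at 57). That is a further reason to state the margin as one number.

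Finally, the worked example is close to the boundary (p = 0.048), and the general t-test might reveal that difference. The example still shows opposite non-inferiority verdicts. The normality and logistic-regression points are secondary, and the conclusion does not depend on them.

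**Conclusion.** The concern holds and must be fixed. The sample size is right for its own inputs, and the plan does contain a margin. The fault is that the primary decision rule uses neither the margin nor the test on which the trial was sized. At the planning values, the four readings run from 0.3% to 34% error and from 66% to 99.7% power at 49 per arm, against a planned 2.5% and 90%. No reading guarantees the planned pair. These figures assume normal data, SD 1.6, an oxygen mean of 3.5 and a fixed deficit of 1.05. The 57-per-arm results also assume no losses, so the 49-per-arm results are the main ones.

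**What to change.** Replace the two lactate sentences in Statistical Analysis with text such as:

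> Umbilical artery lactate will be compared by the difference in means (room air minus oxygen) with a two-sided 95% CI. Room air is non-inferior if the upper limit is below [one number] mmol/L. This analysis governs lactate whatever the Kolmogorov-Smirnov result; the Mann-Whitney test is supportive only. The same rule applies to the per-protocol set.

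State the margin as one number, and make Sample size analysis agree with it. A margin of 1.05 reproduces N = 98, with about 90% power at 49 per arm and 93% at 57. If 1.0 is kept, restate power as about 86% at 49 per arm and 91% at 57; 90% power would need 110 evaluable of the 114.

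Secondary: if an adjusted lactate analysis is wanted, use a linear model on arm plus prespecified baseline covariates already collected, for example parity, growth restriction and pre-intervention deceleration type. Keep logistic regression for binary outcomes, since it does not model continuous lactate.

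Cost: with a margin of 1.05, SAP wording only and no extra patients. With 1.0, either accept and state the lower power or have almost no losses among the 114.

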## Specific Aims

Maternal oxygen administration for concerning fetal heart rate tracing (FHT) patterns is common practice on Labor and Delivery units in the United States. Despite the broad use of oxygen, it is unclear if this practice is beneficial for the fetus. Category II FHT, as defined by the National Institute of Child Health and Human Development (NICHD), is a broad class of FHT patterns that may suggest cord compression and/or placental insufficiency for which oxygen is most commonly administered. Although some animal and human studies have demonstrated that maternal hyperoxygenation can alleviate such fetal heart rate decelerations, this purported benefit has not been shown to translate into improved fetal outcomes, particularly in relation to acid-base status. In fact, some studies suggest harm with oxygen use due to lower umbilical artery pH and increased delivery room resuscitation or increased free radical activity. Given the indeterminate evidence for this ubiquitously employed resuscitation technique, there is an urgent need to further study the utility of maternal oxygen administration in labor for fetal benefit.

We propose a randomized controlled non-inferiority trial comparing oxygen to room air in patients with Category II FHT. Our central hypothesis is that room air alone is not inferior to oxygen administration with regard to neonatal acid-base status and FHT and may in fact, be a safer option for resuscitation due to less production of reactive oxygen species.

**Primary Aim: Determine the effect of maternal oxygen administration for Category II FHT on arterial umbilical cord lactate.**

*Hypothesis: Room air, as a substitute for oxygen supplementation, is no different than oxygen in altering the acid-base status of the neonate as reflected in umbilical arterial (UA) lactate.*

Fetal hypo-oxygenation, as reflected by decelerations in the FHT, results in metabolic acidosis due to a shift from aerobic to anaerobic metabolism in which lactate and hydrogen ion production significantly increase causing a decrease in pH. Elevated umbilical cord lactate has been shown to be a surrogate for fetal metabolic acidosis and resultant neonatal morbidity. The primary outcome will be umbilical arterial (UA) lactate, and secondary outcomes will be other components of a UA gas.

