### **Significant and Potential Impact**

Current practice on our Labor and Delivery is maternal oxygen administration in the presence of Category II FHT for the duration of labor. This practice is unproven in benefit thus far and in fact, some studies suggest harm. Although it may improve fetal oxygenation, evidence thus far does not show an improvement in fetal acid-base status which ultimately correlates with neonatal outcomes. Our study has the potential to create a paradigm shift in intrauterine fetal resuscitation and has significant clinical implications for the fetus and mother. No prior clinical trials in this setting have used cord lactate as a primary outcome. Umbilical cord lactate is an established marker of asphyxia and predictor of neonatal morbidity and serves as a useful assessment of the benefit, or lack thereof, of oxygen for fetal resuscitation. Prior studies have mainly evaluated cord pH as the primary outcome which not only falls behind lactate as a predictor of neonatal outcomes, but also does not serve as an accurate reflection of the degree of metabolic acidosis that may be present due to hypooxygenation. Furthermore, previous trials addressing oxygen administration for similar indications have not employed a similar three-pronged approach to evaluating outcomes via neonatal acid-base status, FHT patterns, and free radical activity. If our stated hypothesis is proven, room air may be an equally efficacious, safer, and cost saving alternative to oxygen. Additionally, it would pave the way for further investigation into the most effective strategies for intrauterine fetal resuscitation.

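### The decision rule for cord lactate offers only two verdicts, defines neither and has no inconclusive category

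*Combined protocol and SAP*

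**What the plan says.** The Statistical Analysis section states that "95% confidence intervals (CI) will be calculated for the mean cord lactate levels in each group", and then: "Comparison of the 95% CI in each group will then determine non-inferiority or inferiority". This is the only decision rule for the primary outcome. It names no interval for the difference between arms, no threshold for either verdict and no third outcome.

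The Sample size analysis section describes a different procedure: a one-sided two-sample t-test at alpha 0.025 with 90% power. It gives the margin twice. The sample size is chosen to "detect a non-inferiority margin of 30" per cent, and the margin is also "therefore set at a lactate cut-off of 4.5, above which there is a clear association with neonatal morbidity".

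The formal hypothesis in that section is that room air is not inferior. Other sections go further. The primary hypothesis in Specific Aims reads "Room air, as a substitute for oxygen supplementation, is no different than oxygen in altering the acid-base status", and Significant and Potential Impact says that, if the hypothesis is proven, "room air may be an equally efficacious, safer, and cost saving alternative to oxygen".

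**The concern.** A non-inferiority trial can end in more than two ways. The interval for the difference may lie below the margin, lie above it, or contain it. An interval that contains both 0 and the margin shows neither that room air is acceptable nor that it is worse. A rule with two labels and no criterion forces such a result into one of them, and the choice could be made after the data are seen.

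The trial's headline conclusion is at stake. One choice reports that withholding oxygen is inferior without evidence that it is. The other reports non-inferiority that the planned test did not show. A positive result also risks being read as equality, which a one-sided non-inferiority test cannot establish.

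**Working it through.** **Inputs.** From Sample size analysis: oxygen mean 3.5 and SD 1.6 mmol/L, margin 30%, one-sided alpha 0.025, power 90%, 98 evaluable patients, 114 after allowance for dropout and crossover. From Strategy: a "computer-generated randomization sequence in a 1:1 ratio", hence 49 or 57 per arm. The margin is taken as 0.30 × 3.5 = 1.05 mmol/L. The plan does not state the true difference used for sizing; 0 is assumed.

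**1. Reproduce the plan's figure.** n per arm = 2 × (1.960 + 1.282)² × 1.6² / 1.05² = 48.8, so 49 per arm and 98 in total, as stated. Exact t-test power at 49 per arm is 89.5%. The 4.5 cut-off implies a margin of 4.5 − 3.5 = 1.0. The same formula then gives 53.8, so 54 per arm and 108 in total. The stated 98 therefore rests on the 30% form.

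**2. Width of the 95% CI for the difference.** Half-width = t × 1.6 × √(2/n).
- 49 per arm: 1.985 × 0.323 = 0.64, total width 1.28.
- 57 per arm: 1.981 × 0.300 = 0.59, total width 1.19.

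Both widths exceed 1.05, so one interval can contain both 0 and the margin.

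**3. When non-inferiority is shown.** The observed difference (room air minus oxygen) must be below 1.05 − 0.64 = 0.41 at 49 per arm, or 1.05 − 0.59 = 0.46 at 57. The latter is 0.46 / 3.5 = 13% above the planning mean, so a pass is compatible with a visibly higher room-air mean.

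**4. When the two group intervals overlap.** Each group's half-width is t × 1.6 / √n: 0.46 at 49 per arm and 0.42 at 57. Room air's interval lies wholly above oxygen's only if the observed difference exceeds about 0.92 or 0.85. If the true difference equals the margin, the approximate probability of not exceeding this is:
- 49 per arm: Φ((0.92 − 1.05) / 0.323) ≈ 0.34
- 57 per arm: Φ((0.85 − 1.05) / 0.300) ≈ 0.25

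**5. Both readings side by side.** The table comes from 400,000 simulated trials per scenario with normal data and SD 1.6. True differences other than 0 and the margin are assumptions, shown as a range. Each cell gives 49 / 57 per arm, in % of all trials. Overlap means that room air's interval does not lie wholly above oxygen's.

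| True difference, mmol/L | Non-inferiority not shown | CI contains both 0 and margin | Group CIs overlap | Not shown, yet CIs overlap |
|---|---|---|---|---|
| 0 | 10.5 / 6.5 | 8.0 / 4.0 | 99.7 / 99.7 | 10.2 / 6.2 |
| 0.35 | 42.7 / 36.2 | 23.9 / 15.1 | 95.6 / 94.8 | 38.3 / 31.0 |
| 0.525 | 63.8 / 58.9 | 27.5 / 17.8 | 88.1 / 85.3 | 51.8 / 44.1 |
| 0.70 | 81.3 / 78.9 | 24.0 / 15.1 | 74.2 / 68.3 | 55.5 / 47.1 |
| 1.05 | 97.5 / 97.5 | 8.0 / 4.1 | 34.0 / 25.2 | 31.6 / 22.7 |

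With identical arms, essentially no trial has a lower limit above the margin. Calling the 10.5% or 6.5% inferior would therefore be unsupported. Under the overlap reading, 10.2 of those 10.5 points (6.2 of 6.5) would be called non-inferior although the planned test did not show it.

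**The case against.** The strongest reply is that the plan never says a trial failing non-inferiority will be reported as inferior. This is correct. A reader might infer that from a two-way rule, but the sentence sets no criterion, and comparing the two group intervals points at least as naturally to overlap, under which the error runs the other way. The documents do not settle the direction of the mislabelling.

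Three further replies also stand.
- A reader might infer that the plan has no correct name for a result that is not worse by more than the margin. It has one: that is what non-inferiority means, and a margin is given.
- A reader might infer that a benefit of room air could never be shown. The general t-test or Mann-Whitney comparison at p<0.05 could show it, and such a result would also be correctly labelled non-inferior. What is missing is a superiority step tied to the lactate verdict.
- The equality phrases are mostly pre-trial hypotheses, and the impact statement is conditional. They are loose wording and not an analysis rule.

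It is also fair to say that 10.5% is simply one minus the power. The type II error is acceptable in itself. The fault is that the rule has no label for those trials. None of these replies supplies a criterion or an inconclusive category.

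**Conclusion.** The point holds in this form: the rule allows two verdicts, defines neither, and must mislabel a result whose interval for the difference contains both 0 and the margin. Such results make up 8.0% (49 per arm) or 4.0% (57) of trials with identical arms, and 24% or 15% at a true difference of 0.35 mmol/L. The wider group in which non-inferiority is not shown is 10.5% or 6.5%, and 43% or 36%, respectively. If overlap is the criterion, a room-air arm worse by exactly the margin would be called non-inferior in 34% or 25% of trials, against the planned 2.5%.

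These figures assume normal data, SD 1.6 in both arms and a margin of 1.05; the value 0.35 is an assumption with no source in the documents. A reader might infer that the sample size is also wrong on this account. It is not: 98 reproduces exactly from the 30% margin.

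**What to change.** Replace the decision sentence with verdicts on the two-sided 95% CI for room air minus oxygen, set against one margin stated in mmol/L:

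- Upper limit below the margin: non-inferior.
- Lower limit above the margin: inferior by more than the margin.
- Otherwise: non-inferiority not shown (inconclusive).

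These three exclude one another. State separately whether the interval excludes 0. If the upper limit is below 0, room air is superior; this step is nested in the non-inferiority test and costs no alpha. If the lower limit is above 0, report that lactate is higher on room air, next to the margin verdict. The two statements must stay separate because an interval can lie wholly between 0 and the margin. With 57 per arm and an observed SD of 1.4, for example, its width would be 2 × 1.981 × 1.4 × √(2/57) = 1.04.

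Reconcile the two forms of the margin (1.05 and 1.0) before the data are analysed. Word a positive result as not worse by more than the margin, and amend the equality wording in Significant and Potential Impact and in the hypotheses to match.

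The cost is a few sentences, with no extra data and no alpha. The one possible consequence for size is that, if the margin is settled at 1.0, 108 evaluable patients are needed for 90% power instead of 98.

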## **Data Collection**

The patient's primary nurse will perform real-time documentation of oxygen initiation, any disruption in intervention, administration of amnioinfusion and additional resuscitation techniques performed (number of times patient is repositioned, total intravenous fluids, discontinuation of oxytocin). Study staff will collect data from medical records on:

- 1) Antepartum history:
  - a. Demographic data: Maternal age, race
  - b. Obstetric history: parity, prior cesarean, gestational age at delivery
  - c. Medical history: BMI at initial prenatal visit, diabetes, chronic hypertension, severe anemia (Hemoglobin <7), tobacco use, illicit drug use
  - d. Prenatal course: diagnosis of hypertensive disorders, gestational diabetes, abruption, intrauterine growth restriction, oligohydramnios
- 2) Intrapartum data:
  - a. Indication for admission/induction
  - b. Oxytocin (duration, total received dose)
  - c. Analgesia
  - d. Duration of labor (first and second stage)
  - e. Diagnosis of chorioamnionitis
  - f. Mode of delivery
  - g. Indication for cesarean
  - h. Electronic fetal monitoring
- 3) Neonatal course:
  - a. APGARs
  - b. Neonatal weight

- c. Admission to special care nursery (SCN) or neonatal intensive care unit (NICU)
- d. Duration of admission to SCN or NICU
- e. Diagnosis of any of the following: hypoxic ischemic encephalopathy, respiratory distress syndrome, oxygen requirement, requirement of hypothermia therapy, seizures, sepsis or suspected sepsis, neonatal death

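### The chorioamnionitis subgroup is not limited to diagnoses made before randomization, so its interaction test can include members defined after treatment starts

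*Combined protocol and SAP*

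**What the plan says.** In the Statistical Analysis section the subgroup list opens with "Additional interaction analyses for the primary outcome will be performed for the following subgroups". The primary outcome is umbilical artery lactate. Items 2 to 5 are fetal tracing features, and each is tied to the period before the intervention, for example "Recurrent late decelerations pre intervention" and "5) Fetal tachycardia pre intervention". Item 7 reads only "7) Chorioamnionitis", with no time reference.

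The Data Collection section introduces the chart items with "Study staff will collect data from medical records on". Under intrapartum data it lists "Diagnosis of chorioamnionitis", between duration of labor and mode of delivery. It asks for no date or time of diagnosis.

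The Strategy section places randomization in active labor, at 6 cm dilation or more, once a Category II tracing calls for resuscitation. Assigned management then applies for the rest of labor, including a cesarean delivery.

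**The concern.** A treatment-by-subgroup interaction can be read as a randomized comparison when membership is fixed before assignment. Here labor continues after randomization, so a patient can enter the subgroup while already under assigned management.

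Two features of the plan make it unsafe to assume that membership is independent of arm. First, Secondary Aim #1 in Specific Aims sets out to study whether oxygen changes resolution of Category II tracings and mode of delivery, especially cesarean for non-reassuring status. If assignment changes when a patient delivers, it also changes how long an intrapartum diagnosis can still be made. Second, the text describes blinding only for the investigator who reads tracings. One arm wears a mask and no sham is described for the other, so the clinicians who make the diagnosis would know the assignment.

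If either route operates, an apparent interaction could partly reflect who was diagnosed and not a different effect of oxygen. Even if neither does, a diagnosis made later was not available when resuscitation was chosen. The subgroup would then not be one that a clinician could identify at that moment.

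**Working it through.** **Reading the sections together**

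| Question | Section | Answer |
|---|---|---|
| Are items 2 to 5 limited in time? | Statistical Analysis | Yes, to before the intervention |
| Is item 7 limited in time? | Statistical Analysis | No |
| Is a time of diagnosis collected? | Data Collection | None listed |
| Can a diagnosis follow randomization? | Strategy | Yes; randomization is in active labor and labor continues |
| Is assignment known to have no effect on delivery? | Specific Aims | No; mode of delivery is an outcome under study |

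Applied as written, the plan counts a diagnosis made at any time in labor. Item 8 (duration of oxygen exposure) is also settled after randomization, but it is a comparison within the oxygen group and not a treatment interaction, so it is not part of this point.

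**Precision of the subgroup analysis**

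The documents give no figure for this subgroup. The inputs that can be checked are those of the Sample size analysis: mean lactate 3.5, SD 1.6, margin 30% × 3.5 = 1.05 mmol/L, one-sided alpha 0.025, power 90%.

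n per arm = 2 × (1.960 + 1.282)² × 1.6² / 1.05² = 48.8, rounded up to 49, or 98 in total. This matches the plan.

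Now take N = 114, SD 1.6, 1:1 allocation within each stratum, and an **assumed** prevalence p:

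SE of interaction = 1.6 × √(4/(Np) + 4/(N(1 − p)))

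Detectable interaction (80% power, two-sided 0.05) = (1.960 + 0.842) × SE

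| Assumed p | Members | SE (mmol/L) | Detectable (mmol/L) |
|---|---|---|---|
| 5% | 5.7 | 1.38 | 3.85 |
| 10% | 11.4 | 1.00 | 2.80 |
| 15% | 17.1 | 0.84 | 2.35 |
| 20% | 22.8 | 0.75 | 2.10 |

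**Possible size of a bias**

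A simulation of 2 million patients per scenario had no true effect of treatment on lactate. A latent factor had correlation 0.5 with lactate and also raised the chance of diagnosis (log-odds 0.8 per SD). All of these settings are assumptions.

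| Diagnosis rate by arm | Difference in lactate, diagnosed | Difference, not diagnosed | Interaction |
|---|---|---|---|
| 12% and 12% | 0.011 | 0.002 | 0.010 |
| 12% and 18% | −0.048 | −0.031 | −0.017 |
| 12% and 26% | −0.086 | −0.071 | −0.016 |

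The true values in the first row are zero, so 0.010 indicates the simulation noise. When treatment changes the diagnosis rate, both strata shift in the same direction and most of the shift cancels in the interaction. The remaining 0.016 is about 2% of the SE of 1.00 at 10% prevalence.

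**The case against.** The strongest reply is that bias needs assignment to change who is diagnosed, and no section says that oxygen affects chorioamnionitis or the length of labor. Where the diagnosis rate is equal in both arms, the simulated within-stratum differences are about zero. Even where treatment doubles the rate, the interaction moves by only about 0.02 mmol/L. The analysis is one of several additional ones. At an assumed 10% prevalence it could detect only an interaction of about 2.8 mmol/L, against a mean lactate of 3.5. All of this stands, and it keeps the point minor. It does not supply the missing time limit, and one assumed simulation cannot show that the bias is small in this trial.

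Two stronger readings are tempting, and the documents do not support either.

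- A reader might infer that the hypertensive subgroup has the same fault, because preeclampsia can first be diagnosed in labor. However, Data Collection records hypertensive disorders under the prenatal course within antepartum history, and Statistical Analysis places them under chronic medical conditions. As planned, that variable comes from before randomization.
- A reader might infer that late diagnoses would dominate the subgroup estimate. That would rest on an assumed incidence and an assumed share of late diagnoses. A count of late-defined members is also not a measure of bias.

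**Conclusion.** The point holds as a minor one. Item 7 lacks the time limit that the plan applies to items 2 to 5, and as written it conditions a treatment-interaction test on a diagnosis that can arise after assignment. Loss of comparability within the subgroup is conditional: it requires that assignment affects the timing or mode of delivery, or who is diagnosed. The protocol leaves the effect on mode of delivery open and shows none of these effects.

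The size of any bias is therefore unknown and may be small. The shift of about 0.02 mmol/L and the SE range of 0.75 to 1.38 mmol/L rest on assumed prevalences (5% to 20%) and an assumed diagnosis model. The intention-to-treat comparison of lactate and the sample size of 98, raised to 114, are not affected.

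**What to change.** Define item 7 as chorioamnionitis diagnosed before randomization. Add the charted time of diagnosis to the intrapartum data and compare it with the time of randomization. Patients diagnosed later then belong to the comparison stratum, which is their status at assignment. Report later diagnoses descriptively by arm. That also gives a direct, though imprecise, look at whether assignment is related to diagnosis.

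The change needs one phrase in the plan and one more chart item, and it depends on the diagnosis time being charted reliably. The statistical cost is precision. If prevalence were 10% and half of the diagnoses came after randomization (both assumed), the subgroup would fall from about 11 to about 6 patients and the SE of the interaction would rise from 1.00 to 1.38 mmol/L. That is a real loss in an already imprecise analysis, accepted so that the result has a randomized interpretation. No change to the primary analysis or the enrollment target is needed.
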